**Table 15.3.2 16: Treated Set- Serious AE- Reason for seriousness (patient based; multiple answers possible)**

Reason for serious AE	N	%
sae.criteria_fatal		
Fatal		
sae.criteria_life_threatening		
Life threatening		
sae.criteria_disability		
Sustained or significant disability/incapacity		
sae.criteria.hospital		
Hospitalization required		
sae.criteria_prolonged		
Hospitalization extended		
sae.criteria_congenital		
Congenital anomaly		
sae.criteria_other		
Otherwise medically significant		
Number of patients with serious AE		

**Table 15.3.2 17: Treated Set- Serious AE by MedDRA system organ class and preferred term- Maximum NCI grade per patient**

sae.nci		Grade 1		Grade 2		Grade 3		Grade 4		Grade 5		Total	
Serious AE- Maximum grade per patient		N	%	N	%	N	%	N	%	N	%	N	%
Any SOC													
SOC1	PT1												
	PT2												
	...												
SOC2	PT1												
	PT2												
	...												
...	PT1												
	PT2												
	...												
No. of patients in Treated Set													

**Table 15.3.2 18: Treated Set- Serious AE- Worst outcome per patient**

sae.outcome; sae.sae	N	%
Serious AE- Outcome		
Recovered/Resolved		
Not yet recovered/resolved		
Recovered/resolved with sequelae		
Fatal		
Unknown		
No serious AE		
No. of patients in Treated Set		

Order: From best to worst: Recovered/resolved; Recovered/resolved with sequelae; Not recovered/Not resolved; Unknown; Fatal

**Table 15.3.2 19: Treated Set- Serious AE- Action taken concerning treatment (patient based; multiple answers possible)**

sae.nci; sae.spolto_action_taken	N	%
Serious AE- Action taken		
Continued		
Reduced		
Stopped		
Increased		
Missing		
No. of patients with serious AE		

**Table 15.3.2 20: Treated Set- Serious AE leading to treatment discontinuation by MedDRA system organ class and preferred term**

sae.nci		N	%
Serious AE leading to discontinuation (patient based)			
Any SOC			
SOC1	PT1		
	PT2		
	...		
SOC2	PT1		
	PT2		
	...		
...	PT1		
	PT2		
	...		
No. of patients in Treated Set			

**Table 15.3.2 21: Treated Set- Serious AE- Number of patients with at least one serious AE with causal relationship to treatment**

sae.causality	N	%
Serious AE- Relationship		
No		
Yes		
Missing		
Total		

**Table 15.3.2 22: Treated Set- Serious AE by relationship with Spiolto® Respimat® by MedDRA system organ class and preferred term**

sae.nci; sae.spiolto_causality		Not related		Related		Total	
Serious AE by relationship (patient based)		N	%	N	%	N	%
Any SOC							
SOC1	PT1						
	PT2						
	...						
SOC2	PT1						
	PT2						
	...						
...	PT1						
	PT2						
	...						
No. of patients in Treated Set							

**2.3 Sensitivity analysis I- Time between Visit 1 and Visit 2**

**Sensitivity analysis- Table 1: Full Analysis Set- Time between Visit 1 and Visit 2 [weeks]**

Anamnesis.date.; visit.date	N	Mean	Std	Min	Median	Max	Nmiss
Sensitivity analysis I- Time between Visit 1 and Visit 2							

**Sensitivity analysis- Table 2: Full Analysis Set- Time between Visit 1 and Visit 2 [categorical]**

Anamnesis.date.; visit.date	N	%
Sensitivity analysis I- Time between Visit 1 and Visit 2 [categorical]		
< 4 weeks		
4-8 weeks		
> 8 weeks		
Patients in FAS		

**Sensitivity analysis- Table 3: Analysis stratified by time between Visit 1 and Visit 2- Full Analysis Set- Total CCQ score- Share of patients with therapeutic success after 6 weeks (approximately)- defined as 0.4-point decrease of total CCQ score between baseline and week 6 (approximately)**

CCQ		N	%	CI 95%
Sensitivity analysis I- Share of patients with therapeutic success				
< 4 weeks	Therapy successful			
	Therapy not successful			
	Missing			
	Total			
4-8 weeks	Therapy successful			
	Therapy not successful			
	Missing			
	Total			
> 8 weeks	Therapy successful			
	Therapy not successful			
	Missing			
	Total			
Total	Therapy successful			
	Therapy not successful			
	Missing			
	Total			

**Sensitivity analysis- Table 4: Analysis stratified by time between Visit 1 and Visit 2- Full Analysis Set- Total CCQ score- Share of patients with therapeutic success-  $\chi^2$ -Test (Fisher's Exact test)**

Therapy success	p-Value
$\chi^2$ -Test (Fisher's Exact test)	

**Sensitivity analysis- Table 5: Analysis stratified by time between Visit 1 and Visit 2- Full Analysis Set- CCQ score**

CCQ			N	Mean	CI 95%	Std	Min	Median	Max	Nmiss	
Sensitivity analysis I- CCQ score											
Baseline (Visit 1)	Symptom	< 4 weeks									
		4-8 weeks									
		> 8 weeks									
		Total									
	Functional state (CCQ-4)	< 4 weeks									
		4-8 weeks									
		> 8 weeks									
		Total									
	Mental state	< 4 weeks									
		4-8 weeks									
		> 8 weeks									
		Total									
	Total CCQ score	< 4 weeks									
		4-8 weeks									
		> 8 weeks									
		Total									
Week 6 (appr.) (Visit 2)	Symptom	< 4 weeks									
		4-8 weeks									
		> 8 weeks									
		Total									
	Functional state (CCQ-4)	< 4 weeks									
		4-8 weeks									
		> 8 weeks									
		Total									
	Mental state	< 4 weeks									
		4-8 weeks									
		> 8 weeks									
		Total									
	Total CCQ score	< 4 weeks									
		4-8 weeks									
		> 8 weeks									
		Total									

**2.4 Sensitivity analysis II- Non-estimated number of exacerbations\***

\*If the physician does not know the exact number of exacerbations he is allowed to give an estimate. In this analysis only those documentations are considered in which the physician knew the exact number, i.e. the number is not estimated (non-estimated).

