GOLD group	Definition	Exacerbations* per year {anamnesis.exacerbation} and/or hospitalizations due to exacerbations {anamnesis_exacerbation_hospital}	mMRC classification {mmrc.activity}
A		0-1 and =0	≤1
B	Low risk, more symptoms	0-1 and =0	≥ 2
C	High risk , less symptoms	≥ 2 or ≥1	0-1
D	High risk , more symptoms	≥ 2 or ≥1	≥ 2

\*For unknown number of exacerbations "0" is included in the calculation of the GOLD group

If 0 or 1 exacerbation per year is documented along with a mMRC of at least grade 2 at baseline the patient is assigned GOLD group B.

If two and more exacerbations per year are documented along with a mMRC of grade 0 or 1 at baseline the patient is assigned GOLD group C.

If two and more exacerbations per year are documented along with a mMRC of at least grade 2 at baseline the patient is assigned GOLD group D.

Duration between initial diagnosis of COPD and baseline visit: Year of Visit 1 {year(anamnesis.date)}- Year of initial COPD diagnosis {anamnesis.copd\_year}

Time between start of treatment and end of observation/discontinuation [weeks]: (Date of Visit 2 {visit.date}/Date of last treatment within observation period {visit.spioalto\_last\_date}- Date of start of treatment {anamnesis.spioalto\_date})/7

Time between Visit 1 and Visit 2 [weeks]: (Date of Visit 2 {visit.date}-Date of Visit 1 {anamnesis.date})/7

Pack years: (Years of smoking)\*(Cigarette parcels per day){anamnesis.smoker\_pack\_years; visit.smoker\_pack\_years}

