**Sensitivity analysis- Table 6: Full Analysis Set- Patients with non-estimated number of exacerbations**

anamnesis.estimate	N	%
Sensitivity analysis II- Non-estimated number of exacerbations		
No		
Yes		
Patients in FAS		

**Sensitivity analysis- Table 7: Full Analysis Set- Patients with non-estimated number of exacerbations- Exacerbations in the last 12 months**

anamnesis.exacerbation	Number of patients	Number of exacerbations	Mean	SD	Min	Median	Max	Nmiss	Patients with event	
									N	%
Sensitivity analysis II- Exacerbations in the last 12 months										

**Sensitivity analysis- Table 8: Full Analysis Set- Patients with non-estimated number of exacerbations- Exacerbations in the last 12 months [categorical]**

anamnesis.exacerbation;	N	%
Sensitivity analysis II- Exacerbations in the last 12 months- Overview		
No		
Yes		
Patients in FAS with non-estimated number of exacerbations		

**Sensitivity analysis- Table 9: Full Analysis Set- Patients with non-estimated number of exacerbations- COPD degree of severity (GOLD group)**

Non-estimated number of exacerbations- COPD degree of severity (GOLD group)	N	%
A		
B		
C		
D		
Missing		
Patients in FAS with non-estimated number of exacerbations		

**Sensitivity analysis- Table 10: Full Analysis Set- Patients with non-estimated number of exacerbations- COPD degree of severity (GOLD group) [grouped]**

		N	%
Sensitivity analysis II- COPD degree of severity (GOLD group) [grouped]			
A/B			
C/D			
Missing			
Patients in FAS with non-estimated number of exacerbations			

**Sensitivity analysis- Table 11: Full Analysis Set- Patients with non-estimated number of exacerbations- COPD degree of severity (GOLD group) – Distribution**

		A		B		C		D		Missing	
Sensitivity analysis II- GOLD stadium- Distribution		N	%	N	%	N	%	N	%	N	%
Symptoms	Exacerbations										
0-1	0-1										
	>=2										
2-4	0-1										
	>=2										
Patients in FAS with non-estimated number of exacerbations											

**Sensitivity analysis- Table 12: Full Analysis Set- Patients with non-estimated number of exacerbations- Total CCQ score- Share of patients with therapeutic success after 6 weeks (approximately)- defined as 0.4-point decrease of total CCQ score between baseline and week 6 (approximately)**

CCQ		N	%	CI 95%
Sensitivity analysis II- Share of patients with therapeutic success				
Gold A	Therapy successful			
	Therapy not successful			
	Missing			
	Total			
GOLD B	Therapy successful			
	Therapy not successful			
	Missing			

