**Listing 3: Treated Set- GOLD group**

org. name; org.city	patient.no	mmrc.act ivity	anamnesis.exacerb ation	anamnesis.estimate	anamnesis.exacerb ation_hospital	anamnesis.estimate_ho spital	
Site	Patient- No.	mMRC classifica tion	Exacerbations within the last 12 months before initial visit	Number of exacerbations estimated?	Hospitalizations due to exacerbations	Number of hospitalizations due to exacerbations estimated?	GOLD group

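### Sensitivity analysis II removes estimated exacerbation counts but not estimated hospitalisation counts, although its Tables 9 to 13 report by GOLD group, which depends on both

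*SAP*

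**What the plan says.** SAP 2.4 explains why the analysis exists: "If the physician does not know the exact number of exacerbations he is allowed to give an estimate". It then limits the set: "In this analysis only those documentations are considered in which the physician knew the exact number, i.e. the number is not estimated (non-estimated". Table 6 of that section names one field for the selection, "anamnesis.estimate". Tables 8 to 11 use the denominator "Patients in FAS with non-estimated number of exacerbations", and Tables 7, 12 and 13 carry the same restriction in their titles.

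Listing 3 (SAP 2.7) prints a second flag, `anamnesis.estimate_hospital`, beside the first, with the column title "Number of hospitalizations due to exacerbations estimated". No table in 2.4 refers to it.

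The GOLD table in SAP section 1 takes "hospitalizations due to exacerbations {anamnesis_exacerbation_hospital" as an input next to the exacerbation count. It assigns C or D when there are at least two exacerbations or at least one hospitalisation. The prose under that table gives the rule for group C as "If two and more exacerbations per year are documented along with a mMRC of grade 0 or 1 at baseline", words the rule for D in the same way, and mentions no hospitalisation route for either.

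**The concern.** The set is cleaned on one of two history variables that may be estimated, but the results shown in it are arranged by a classification built from both. A patient with exactly one known exacerbation, an estimated single hospitalisation and mMRC grade 2 passes the filter and is counted in D; with no hospitalisation the same patient would be in B. The error can also run the other way, since an estimated zero can hold a patient in A or B.

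B against C/D, and B against C against D, are subgroup comparisons of the primary outcome that both the protocol abstract and SAP 2.5 specify. For patients with one exacerbation, the hospitalisation count decides which side of that boundary they fall on. If Tables 9 to 13 agree with the main GOLD results, a reader may take this as robustness to estimated history while some assignments still rest on estimates.

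**Working it through.** **Inputs**
- Selection field: `anamnesis.estimate` (SAP 2.4, Table 6).
- Unused flag: `anamnesis.estimate_hospital` (SAP 2.7, Listing 3).
- Tabular rule (SAP section 1), with E exacerbations and H hospitalisations: high risk if E ≥ 2 or H ≥ 1. High risk gives C at mMRC 0–1 and D at mMRC 2–4; otherwise A and B respectively.
- Planned analysable patients: 1170 (Protocol 9.5).

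**Step 1: the plan's own figures.** None is given for Sensitivity analysis II. The base of 1170 is consistent within Protocol 9.5: 1170 / (1 − 0.10) = 1300, and 0.5 ± 1.96 × √(0.25/1170) gives 47.13% to 52.87%, against 47.1% to 52.9% stated.

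**Step 2: where the group depends on H when E is exact.** Assume that hospitalised events are counted within the exacerbation total, so H ≤ E. Protocol Table 9.2.3.1 describes the second item as exacerbations that led to hospitalisation, which fits this, but neither document states it as a rule.

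| Exact E | Possible H | Group at mMRC 0–1 | Group at mMRC 2–4 | Depends on H? |
|---|---|---|---|---|
| 0 | 0 | A | B | No |
| 1 | 0 | A | B | Yes |
| 1 | 1 | C | D | Yes |
| 2 or more | 0 to E | C | D | No |

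Only E = 1 is exposed. If hospitalisations could be recorded outside the exacerbation total, E = 0 would be exposed as well.

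**Step 3: does the filter catch it?** No. A record with exact E = 1 passes on `anamnesis.estimate`, whatever `anamnesis.estimate_hospital` says.

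**Step 4: which outputs are touched.** Tables 6 to 8 contain no GOLD group. Tables 9 to 11 show the GOLD distribution, and Tables 12 and 13 show success and CCQ scores by group. The Total rows of Tables 12 and 13 do not depend on GOLD assignment.

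**Step 5: size.** The documents give no share. With an assumed range of 1% to 10% of 1170: 0.01 × 1170 = 11.7, about 12; 0.10 × 1170 = 117.

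**Step 6: table against prose.** Under the prose rule E = 1 gives A or B whatever H is, so the problem would not arise. Table 11 also cross-tabulates GOLD group by symptoms and by exacerbations (0–1 against 2 or more) without hospitalisations. If the tabular rule is programmed, any patient in column C or D of a 0–1 exacerbation row got there through hospitalisation alone. Those cells therefore cap the number moved upward by an estimated hospitalisation count, though not the number held down by an estimated zero.

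**The case against.** The strongest reply is that section 2.4 does what its title says. It promises exactness for the number of exacerbations only, and the table titles repeat that limit. Nowhere does the SAP call the hospitalisation count or the GOLD group exact. This stands: the filter does not contradict its own definition. The gap is that results are shown by a classification that the filter only partly covers.

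A second reply is that the affected cell is probably small, because the physician must know that there was exactly one exacerbation and yet have to estimate whether it led to admission. That is plausible, and no figure in the documents settles it. Listing 3 also prints both counts, both flags and the GOLD group for each treated patient, so affected records can be found afterwards.

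A reader might further infer that the flag will be applied the wrong way round. The field answers whether the number was estimated, while Table 6 lists No and Yes under a non-estimated heading. The documents do not support that as a planning error. Section 2.4 defines the set in words, and the SAP's introduction presents field names as pointers to where data are found, not as selection code. It is a label worth clarifying.

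**Conclusion.** The point holds for the GOLD-based content of Tables 9 to 13 and is a low-cost improvement. It rests on the tabular GOLD rule and, for the narrow cell of one exact exacerbation, on hospitalised events being part of the exacerbation total. The range of about 12 to 117 patients illustrates an assumed 1% to 10% share; it is not an estimate from the documents.

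A reader might infer that the whole sensitivity analysis or the primary result is compromised. Neither follows. The primary success proportion does not use GOLD group, Tables 6 to 8 are correctly defined by the exacerbation flag, and the Total rows do not depend on GOLD assignment.

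One limit would remain after the change. SAP section 1 enters zero for an unknown number of exacerbations, and the documents do not say how the estimate flag is set for those records, so the groups may still contain assumed values.

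**What to change.** In SAP 2.4, define the set for Tables 9 to 13 as patients for whom both `anamnesis.estimate` and `anamnesis.estimate_hospital` indicate that the number is not estimated, and adjust those titles and denominators. Leave Tables 6 to 8 on the exacerbation flag alone; the second flag would drop patients there whose exacerbation count is exact.

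Two minor clarifications belong with this. State in Table 6 that non-estimated = Yes corresponds to `anamnesis.estimate` = No. Reconcile the GOLD table in SAP section 1 with the prose beneath it, so that the programmed rule is unambiguous.

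The cost is one sentence, one filter condition and a few labels; the flag is already collected. The downside is a slightly smaller set for Tables 9 to 13, so the denominators of the Total rows in Tables 12 and 13 would also change.

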**Sensitivity analysis- Table 6: Full Analysis Set- Patients with non-estimated number of exacerbations**

anamnesis.estimate	N	%
Sensitivity analysis II- Non-estimated number of exacerbations		
No		
Yes		
Patients in FAS		

**Sensitivity analysis- Table 7: Full Analysis Set- Patients with non-estimated number of exacerbations- Exacerbations in the last 12 months**

anamnesis.exacerbation	Number of patients	Number of exacerbations	Mean	SD	Min	Median	Max	Nmiss	Patients with event	
									N	%
Sensitivity analysis II- Exacerbations in the last 12 months										

**Sensitivity analysis- Table 8: Full Analysis Set- Patients with non-estimated number of exacerbations- Exacerbations in the last 12 months [categorical]**

anamnesis.exacerbation;	N	%
Sensitivity analysis II- Exacerbations in the last 12 months- Overview		
No		
Yes		
Patients in FAS with non-estimated number of exacerbations		

**Sensitivity analysis- Table 9: Full Analysis Set- Patients with non-estimated number of exacerbations- COPD degree of severity (GOLD group)**

Non-estimated number of exacerbations- COPD degree of severity (GOLD group)	N	%
A		
B		
C		
D		
Missing		
Patients in FAS with non-estimated number of exacerbations		

**Sensitivity analysis- Table 10: Full Analysis Set- Patients with non-estimated number of exacerbations- COPD degree of severity (GOLD group) [grouped]**

		N	%
Sensitivity analysis II- COPD degree of severity (GOLD group) [grouped]			
A/B			
C/D			
Missing			
Patients in FAS with non-estimated number of exacerbations			

**Sensitivity analysis- Table 11: Full Analysis Set- Patients with non-estimated number of exacerbations- COPD degree of severity (GOLD group) – Distribution**

		A		B		C		D		Missing	
Sensitivity analysis II- GOLD stadium- Distribution		N	%	N	%	N	%	N	%	N	%
Symptoms	Exacerbations										
0-1	0-1										
	>=2										
2-4	0-1										
	>=2										
Patients in FAS with non-estimated number of exacerbations											

**Sensitivity analysis- Table 12: Full Analysis Set- Patients with non-estimated number of exacerbations- Total CCQ score- Share of patients with therapeutic success after 6 weeks (approximately)- defined as 0.4-point decrease of total CCQ score between baseline and week 6 (approximately)**

CCQ		N	%	CI 95%
Sensitivity analysis II- Share of patients with therapeutic success				
Gold A	Therapy successful			
	Therapy not successful			
	Missing			
	Total			
GOLD B	Therapy successful			
	Therapy not successful			
	Missing			
	Total			
GOLD C	Therapy successful			
	Therapy not successful			
	Missing			
	Total			
GOLD D	Therapy successful			
	Therapy not successful			
	Missing			
	Total			
Total	Therapy successful			
	Therapy not successful			

CCQ		N	%	CI 95%
Sensitivity analysis II- Share of patients with therapeutic success				
	Missing			
	Total			

**Sensitivity analysis- Table 13: Full Analysis Set- Patients with non-estimated number of exacerbations- CCQ score**

CCQ		N	Mean	CI 95%	Std	Min	Median	Max	Nmiss
Sensitivity analysis II- CCQ score									
Baseline (Visit 1)	Symptom	A							
		B							
		C							
		D							
		Total							
	Functional state (CCQ-4)	A							
		B							
		C							
		D							
		Total							
	Mental state	A							
		B							
		C							
		D							
		Total							
	Total CCQ score	A							
		B							
		C							
		D							
		Total							
	Symptom	A							
		B							
		C							
		D							
		Total							
	Functional state (CCQ-4)	A							
		B							
		C							
		D							
		Total							
Mental state	A								
	B								
	C								

CCQ			N	Mean	CI 95%	Std	Min	Median	Max	Nmiss
Sensitivity analysis II- CCQ score										
		D								
		Total								
	Total CCQ score	A								
		B								
		C								
		D								
		Total								

**2.5 Tables for subgroup analysis**

For each of the following subgroups

- Maintenance naïve patients vs. patients already treated at baseline (i.e. before start of therapy with Spiolto® Respimat®) with long-acting bronchodilators (LAMA only or LABA only) or LABA+ICS [Only if both categories include more than 20% of all patients, respectively]
- Maintenance naïve patients vs. patients already treated at baseline with long-acting bronchodilators (LAMA only) vs patients already treated at baseline with long-acting bronchodilators (LABA only) vs patients already treated at baseline with long-acting bronchodilators (LABA+ICS)
- ICS treatment at baseline (Patients with ICS vs. Patients without ICS) [Only if both categories include more than 20% of all patients, respectively]
- GOLD spirometric classifications (Group 1) (1/2 vs. 3/4)
- GOLD spirometric classifications (Group 2) (2 vs. 3 vs. 4)
- GOLD patients group (Group 1) (B vs. C/D)
- GOLD patients group (Group 2) (B vs. C vs. D)
- Age (≤ 65 years vs. >65 years)
- Exacerbations in the last 12 months (≤1 vs. ≥2)
- Hospitalizations due to exacerbations (0 vs. ≥1)
- Smoker (Smoker vs. Ex-Smoker vs. Non-smoker)
- Patients with cardiac comorbidities (No vs. Yes)
- Continuation of Spiolto® Respimat® usage after end of study observation (No vs. Yes)

Table 1 to Table 9 given below will be displayed for each subgroup, respectively, subgroup and group 1, group ... are respective placeholders.

Primary endpoints

**Subgroup analysis- Table 1: Analysis stratified by subgroup- Full Analysis Set- Total CCQ score- Share of patients with therapeutic success after 6 weeks (approximately), defined as 0.4-point decrease of total CCQ score between baseline and week 6 (approximately)**

CCQ		N	%	CI 95%
Share of patients with therapeutic success				
Group 1	Therapy successful			
	Therapy not successful			
	Missing			
	Total			
Group ...	Therapy successful			
	Therapy not successful			
	Missing			
	Total			
Total	Therapy successful			

CCQ		N	%	CI 95%
Share of patients with therapeutic success				
	Therapy not successful			
	Missing			
	Total			

**Subgroup analysis- Table 2: Analysis stratified by subgroup- Full Analysis Set- Total CCQ score- Share of patients with therapeutic success-  $\chi^2$ -Test (Fisher's Exact test)**

X  -Test (Fisher's Exact test) - Therapy success	p-Value
Group 1 vs. Group ...	

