Data analysis:	
Primary outcome: “Therapeutic success” at visit 2 (0.4 - point decrease in the CCQ score from visit 1 to visit 2).
 
Secondary outcomes: Change in the CCQ and CCQ-4 score from visit 1 to visit 2. General condition of the patient, evaluated by the physician (PGE-score) at visit 1 and visit 2 Patient satisfaction with Spiolto® Respimat® at visit 2 Patient’s willingness to continue treatment Subgroup analysis for maintenance naïve patients and the ones already treated at baseline with long acting bronchodilators or LABA + ICS will be performed for the primary outcome. Subgroup analyses will be performed by GOLD spirometric classifications (2 vs. 3 vs. 4) and GOLD patient groups (B vs. C/D and B vs. C vs. D) for the primary outcome and changes in CCQ score for the secondary outcome
		
Milestones:	Start of data collection	Q2 2017	
	End of data collection	Q2 2018	
	Final report of study results	Q3 2018	

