9.5 STUDY SIZE

We assume that patients treated with Spiolto[®] Respimat[®] will have a CCQ therapeutic success rate similar to the SGRQ responder rate. In the TONADO studies^v patients treated with Spiolto[®] Respimat[®] had a 57.5% SGRQ responder rates after 24 weeks.

The TONADO was a selected trial population, so a real world population would probably show somewhat lower numbers due to the wide diversity of potential patients that will be followed up. Therefore a 50% CCQ therapeutic success rate is a reasonable assumption.

Assuming a 50% therapeutic success rate for CCQ and a sample size of 1170 patients, the 95% confidence interval for the therapeutic success rate would be between 47.1% (lower limit) and 52.9% (upper limit).

Subgroups with long acting bronchodilators at baseline (i.e., LABA only, LAMA only, LABA and ICS) will be analyzed only if they include more than 20% of all patients. In the smallest subgroup (with at least 234 patients), assuming a 50% therapeutic success rate, the 95% confidence interval would be between 43.6% and 56.4%.

To account for a 10% drop-out rate, the sample size becomes 1300 patients.

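### SAP 2.5 makes the naive versus pooled pretreated analysis of the primary outcome depend on a 20% naive share that the protocol does not require, while the finer four-group split has no floor

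*SAP*

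**What the plan says.** The protocol abstract (section 4, data analysis) states: "Subgroup analysis for maintenance naïve patients and the ones already treated at baseline with long acting bronchodilators or LABA + ICS will be performed". The sentence refers to the primary outcome and carries no size condition.

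The protocol's only floor is in section 9.5: "Subgroups with long acting bronchodilators at baseline (i.e., LABA only, LAMA only, LABA and ICS) will be analyzed only if they include more than 20" per cent of all patients. Maintenance-naive patients are not in that list. The same section gives the precision at the floor: "In the smallest subgroup (with at least 234 patients), assuming a 50% therapeutic success rate", with a 95% interval of 43.6% to 56.4%.

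SAP section 2.5 has three bullets on prior therapy.

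- Bullet 1, naive against pooled pretreated, is conditional: "LAMA only or LABA only) or LABA+ICS [Only if both categories include more than 20% of all patients, respectively".
- Bullet 2 is the four-group split: naive against LAMA only, "vs patients already treated at baseline with long-acting bronchodilators (LABA only) vs patients already treated at baseline with long-acting bronchodilators (LABA+ICS". It has no condition.
- Bullet 3 writes the condition out again: "ICS treatment at baseline (Patients with ICS vs. Patients without ICS) [Only if both categories include more than 20% of all patients, respectively".

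Because bullet 3 restates the rule, bullet 2 cannot be taken to inherit it from bullet 1.

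**The concern.** The floor sits almost the opposite way round from the protocol. Protocol 9.5 restricts the individual pretreated subgroups and does not mention naive patients. The SAP leaves the individual pretreated subgroups unrestricted and restricts the pooled split, on the naive side as well. Neither document explains the move.

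If 20% or fewer of the patients are naive, bullet 1 is not produced. What goes with it is the pooled pretreated success rate with its interval (Subgroup Table 1), the pooled summaries of CCQ change (Subgroup Table 4) and the two-group comparisons (Subgroup Tables 2 and 5). The protocol's background gives this split a rationale: section 7.2.1 reports that, in the earlier observational study of the free combination, the greatest benefit was in less severe patients and those without prior maintenance treatment. An analysis that the protocol commits to should not drop out under a condition that the protocol does not set for that group.

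**Working it through.** **Inputs.** Protocol 9.5 gives a 50% success rate, 1170 evaluable patients, a floor of 20% (234 patients), and 1300 patients after allowing for 10% drop-out. The documents give no expected naive share, so the shares below are assumptions. Two more assumptions are made: the 20% is taken of 1170, and every patient who is not naive counts as pretreated.

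**The plan's own figures.** Half-width of a 95% interval for one group: 1.96 × √(0.25/n).

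- n = 1170: 2.87 points, so 47.1% to 52.9%, as stated.
- n = 0.20 × 1170 = 234: 6.41 points, so 43.6% to 56.4%, as stated.
- 1170/0.90 = 1300, as stated.

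**Naive against pooled pretreated.** Half-width of the difference: 1.96 × √(0.25/n + 0.25/(1170 − n)).

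| Naive share (assumed) | Naive n | Pretreated n | Naive half-width | Difference half-width | Bullet 1 shown? |
|---|---|---|---|---|---|
| 25% | 292 | 878 | 5.7 | 6.6 | yes |
| 20% | 234 | 936 | 6.4 | 7.2 | no (must exceed 20%) |
| 18% | 211 | 959 | 6.7 | 7.5 | no |
| 15% | 176 | 994 | 7.4 | 8.0 | no |

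Moving from 20% to 15% costs 8.0 − 7.2 = 0.8 points of half-width on the difference.

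**What bullet 2 shows in the same situation.** Take a 15% naive share and three equal pretreated cells of 994/3 ≈ 331 (an illustration). Naive against any one cell has a half-width of 1.96 × √(0.25/176 + 0.25/331) ≈ 9.1 points. The pooled comparison, at 8.0 points, is withheld while these are printed.

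**Bullet 2 against the floor in protocol 9.5.** With a 50/50 split of naive and pretreated, three equal pretreated cells hold 585/3 = 195 patients each, or 16.7%. That is below the floor, with a half-width of 7.0 points. With 15% pretreated (176), equal cells hold about 59 each, with a half-width of 12.8 points. The SAP would report the cells in both cases.

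**The case against.** Several objections stand and limit the point.

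- A reader might infer that the protocol names a two-way contrast and that the SAP can delete it. The protocol does not go that far. The abstract promises a subgroup analysis for these groups; only its next sentence, on GOLD classes, uses versus wording. Protocol 9.7 plans no formal tests, so the two-group p-values are an SAP addition.
- A reader might infer that the naive result would disappear. It would not. Bullet 2 is unconditional, so naive n, rate and 95% interval still appear there, unchanged. The pooled pretreated success count and denominator can be rebuilt by adding three rows, and Listing 5 records naive or pretreated status for each patient.
- It is tempting to say that the rule keeps the least precise results and suppresses the most precise. That is true only of the pretreated side; the naive group is the same in both splits.
- A pretreated-side floor has some support. In protocol 9.5 it is unclear whether the 20% applies to each listed subgroup or to them together. If together, that half of the bullet 1 condition follows the protocol.
- The rule is prespecified and depends on baseline therapy, not on outcome. The protocol's own floor also depends on recruitment shares, so the documents do not support a charge of selective reporting.

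Neither reading of the floor sentence in 9.5 names naive patients. The reference there to a smallest subgroup of at least 234 could be read more widely, but it follows directly on that list.

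**Conclusion.** This is a real but minor mismatch between protocol and SAP. The naive-side 20% condition in bullet 1 has no clear basis in the protocol and can remove an analysis to which the protocol commits. What would be lost is the pooled pretreated interval, the pooled change summaries and the two-group comparison. The naive result would not be lost, nor would the means of rebuilding the pooled success rate.

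Precision is a weak reason for the condition. The half-width of the difference rises only from 7.2 points at a 20% naive share to 7.5 at 18% and 8.0 at 15%, and bullet 2 prints finer comparisons in the same circumstances. These figures rest on 50% success, 1170 evaluable patients and all non-naive patients counting as pretreated. The last assumption is generous, because SAP Table 15.1.4 16 also provides for patients on ICS only. How likely the condition is to bite cannot be judged from the documents.

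**What to change.** In SAP 2.5, bullet 1, remove the 20% condition on the naive side. State that naive against pooled pretreated is always reported for the primary outcome, with n, success rate and 95% confidence interval in each group, and that a small category is flagged.

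Keep a pretreated-side floor only if the sponsor confirms that protocol 9.5 means the pretreated patients together.

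In the same edit, reconcile bullet 2 with the 9.5 floor for the LABA-only, LAMA-only and LABA-plus-ICS cells, or record and justify the departure. The two bullets need to be changed together: if the floor were restored to bullet 2 and bullet 1 left as it is, a naive share of 20% or less could leave no prior-therapy comparison that includes naive patients.

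The cost is a few lines of SAP text and no new data. The only downside is a somewhat wider interval on display when one category is small.
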